6.3.2. Darbepoetin Alfa Dosing Information

Darbepoetin Alfa Starting Dose:

Group 1 (not using ESA): The SC darbepoetin alfa starting dose will be determined based on weight and baseline Hgb. Subjects with baseline (Day 1) Hgb values of 9 to 10 g/dL will be assigned a starting dose of 0.45 µg/kg, with the lowest starting dose being 30 µg to allow for a one dose step decrease, if required, and a top starting dose of 60 µg. Those with baseline (Day 1) Hgb values of 8 to <9 g/dL will receive one dose step higher.

Baseline (Day 1) Hgb (g/dL)	Darbepoetin Alfa Starting Dose	How Delivered
8 to <9	If <78 kg starting dose 40 µg If 78-112 kg starting dose 60 µg If >112 starting dose 80 µg	40 µg every 4 weeks 60 µg every 4 weeks 80 µg every 4 weeks
9 to 10	If <78 kg starting dose 30 µg If 78-112 kg starting dose 40 µg If >112 starting dose 60 µg	30 µg every 4 weeks 40 µg every 4 weeks 60 µg every 4 weeks

Group 2 (ESA users): The starting dose is as follows:

- For subjects already on SC darbepoetin alfa, the starting dose will be the same as their currently scheduled dose, rounded to the nearest study dose.
- For subjects receiving other types of ESAs, the starting dose will be a SC darbepoetin alfa equivalent dose, rounded to the nearest study dose.

Darbepoetin Alfa Dose Steps:

Dose-steps of darbepoetin alfa are pre-defined in this study ([Table 5](#)). Darbepoetin alfa dose adjustments (increases and decreases) are generally within the 20 to 33% range, with a few increases of 50% based on available dose strengths. In some cases, a partial amount of a PFS will be used to deliver the total 4-weekly dose; this information is provided in the SRM. Those receiving the highest dose of darbepoetin alfa who require a dose increase will maintain the same dose, while those receiving the lowest dose of darbepoetin alfa that require a dose decrease will have doses withheld.

Table 5 Darbepoetin Alfa Dose Steps

Total 4-Weekly Dose	PFS Dose and Frequency
20 µg	20 µg every 4 weeks
30 µg	30 µg every 4 weeks
40 µg	40 µg every 4 weeks
60 µg	60 µg every 4 weeks
80 µg	80 µg every 4 weeks
100 µg	100 µg every 4 weeks
150 µg	150 µg every 4 weeks
200 µg	100 µg every 2 weeks
300 µg	150 µg every 2 weeks
400 µg	100 µg once a week

6.3.3. Daprodustat and Darbepoetin Alfa Dose Adjustment Algorithm

The protocol-specified randomized treatment (daprodustat or darbepoetin alfa) dose adjustment algorithm is provided in [Appendix 6](#). Dose adjustments (i.e., increase, decrease, maintain, or withheld if ≥ 12 g/dL) will be made programmatically for both the daprodustat and darbepoetin alfa arms by the IRT system to maintain Hgb concentrations within the range of 10-11 g/dL based on the HemoCue Hgb value measured at least every 4 weeks (Day 1 through Week 52) or at least every 12 weeks (post-Week 52 through end of treatment) disclosed to the IRT system by the investigator.

From Week 52 onwards, additional study visits to check Hgb and dispense randomized treatment (where directed by the IRT system) will be required under the circumstances outlined in [Appendix 6](#).

In order to mitigate subjects remaining below the Hgb target range for an extended period of time, adjustments to the algorithm may be implemented by the sponsor as outlined in [Appendix 6](#) based on the review of blinded instream aggregate Hgb data.

6.3.4. Randomized Treatment Temporary Interruption

Every effort must be made to continue randomized treatment and to complete study visits, where able; however, sites should contact PPD Remote Site Monitor-Local if a subject cannot return to the research site on a temporary basis for any one of the following situations:

- Subjects who are hospitalized for any duration.
- Subjects who cannot return to the site for a period >5 weeks during the first 52 weeks and >13 weeks thereafter.

In exceptional circumstances, local standard of care for anemia management during this time period may be considered based on consultation with the PPD Medical Monitor. If

non-study ESAs are administered, doses should be recorded on the Prior/Concomitant Medications – ESA eCRF page.

6.3.5. Randomized Treatment Discontinuation

The sponsor will inform investigators when they should have subjects come in for an End of Study visit based on the projected occurrence of 664 first MACE. Subjects will stop taking randomized treatment the day of the End of Study visit.

For those subjects who permanently discontinue randomized treatment, see Section 5.5.1 for study visit details.

Anemia therapy may recommence, as required, once randomized treatment has been discontinued.

6.4. Blinding

This is an open-label study; however, the sponsor is blinded to treatment assignment for both the main study and ABPM sub-study. Randomized treatment will have the dose strength on the label. A detailed Blinding Plan will describe the procedures that will be implemented in order to minimize the extent to which this blind may be compromised.

6.5. Packaging and Labeling

Daprodustat tablets are packed in white, opaque high density polyethylene (HDPE) bottles with child-resistant closures. The contents of the label will be in accordance with all applicable regulatory requirements.

6.6. Preparation/Handling/Storage/Accountability

No special preparation of placebo run-in or randomized treatment is required.

Only subjects enrolled in the study may receive placebo run-in and, subsequently, randomized treatment and only authorized site staff may supply placebo run-in and randomized treatment. All placebo run-in and randomized treatment must be stored in a secure environmentally controlled and monitored (manual or automated) area in accordance with the labeled storage conditions with access limited to the investigator and authorized site staff.

The investigator, institution, or the head of the medical institution (where applicable) is responsible for placebo run-in and randomized treatment accountability, reconciliation, and record maintenance (i.e. receipt, reconciliation and final disposition records).

Further guidance and information for final disposition of unused placebo run-in and randomized treatment is provided in the SRM.

Under normal conditions of handling and administration, placebo run-in and randomized treatment are not expected to pose significant safety risks to site staff.

A Material Safety Data Sheet (MSDS)/equivalent document describing occupational hazards and recommended handling precautions either will be provided to the investigator, where this is required by local laws, or is available upon request from GSK.

6.7. Compliance with Randomized Treatment Administration

Randomized subjects who administer randomized treatment (daprodustat or darbepoetin alfa) at home will be instructed to return all unused randomized treatment at each clinic visit. A record of the number of daprodustat tablets or darbepoetin alfa doses dispensed to and taken by each subject will be maintained and reconciled with randomized treatment and compliance records. Randomized treatment start and stop dates and dosing details, including dates for randomized treatment interruptions and/or dose increases or reductions, will be recorded in the eCRF. At Week 2 and for unscheduled visits, compliance checking will not be performed if the dose of randomized treatment is not changed.

For subjects randomized to darbepoetin alfa who have randomized treatment administered in the clinic, the details of each administered darbepoetin alfa dose will be maintained and reconciled with randomized treatment and compliance records. Randomized treatment start and stop dates and dosing details, including dates for randomized treatment interruptions and/or dose increases/reductions, will be recorded in the eCRF.

6.8. Treatment of Randomized Treatment Overdose

There is no specific antidote for overdose with daprodustat. The expected manifestations of daprodustat overdosage include signs and symptoms associated with an excessive and/or rapid increase in Hgb concentration. Daprodustat is highly protein bound; thus, clearance of daprodustat by hemodialysis (HD) or peritoneal dialysis (PD) is very low and these are not effective methods to enhance the elimination of daprodustat. Daprodustat metabolites are, in part, cleared via hemodialysis. In the event of a suspected overdose, it is recommended that the appropriate supportive clinical care be instituted, as dictated by the subject's clinical status. Additionally, subjects should be monitored closely for CV events, increased heart rate and hematologic abnormalities.

Consult the approved product label for information on overdose for darbepoetin alfa.

6.9. Treatment after the End of the Study

Subjects will not receive any additional treatment from GSK after completion of the study. The investigator is responsible for ensuring that consideration has been given to post-study care of the subject's medical condition.

6.10. Concomitant Medications and Non-Drug Therapies

Concomitant medications, including over-the-counter medications and supplements, taken during the study will be recorded in the eCRF. Start/stop dates and route of administration will be recorded for general concomitant medications. Additional details (e.g., changes in dose, reason for change, reason for addition or termination) will be

recorded for certain medications at each visit (e.g., iron and anti-hypertensive medications).

6.10.1. Permitted Medications and Non-Drug Therapies

Unless specified as a prohibited medication in Section 6.10.2, all concomitant medications should be considered permitted provided they are not contraindicated for the individual subject concerned.

Co-administration of daprodustat with moderate CYP2C8 inhibitors (e.g., clopidogrel, teriflunomide, deferasirox) should be performed with caution. If one of these medications is started, stopped or the dose is changed, Hgb should subsequently be monitored every 4 weeks for the following 12 weeks.

6.10.2. Prohibited Medications and Non-Drug Therapies

Use of any of the following prescription drugs from screening (Week -8) until 7 days after the last dose of randomized treatment is prohibited and will constitute a protocol violation.

- Strong inhibitors of CYP2C8 (e.g., gemfibrozil)
- Strong inducers of CYP2C8 (e.g., rifampin/rifampicin)

No other investigational agents or devices are permitted from study entry through completion of the study, with the exception of the randomized treatment administered for this study.

6.11. Standard of Care

During the study (from screening), investigators are expected to monitor the subject's overall clinical status to ensure standards of care are met to enable consistency of practice with Kidney Disease Improving Global Outcomes (KDIGO) guidelines or local equivalent (e.g, phosphate and albumin).

For this study, specific iron management criteria and a dose adjustment algorithm for randomized treatment will apply. These were developed to reflect global clinical practice.

6.11.1. Iron Management Criteria

Subjects must remain iron replete throughout the study. The investigator will follow the iron management criteria from randomization (Day 1) through the end of the study treatment period for subjects receiving randomized treatment.

Iron therapy will be administered if ferritin is ≤ 100 ng/mL and/or TSAT is $\leq 20\%$. The investigator should choose the route of administration and dose of iron based on the subject's iron status and local clinical practice.

All iron (excluding multivitamins) must be stopped and cannot be administered if;

- Ferritin >800 ng/mL and TSAT >20%, or
- TSAT >40%

Investigators should be guided by local/regional guidelines and may stop administration of iron at a lower ferritin or TSAT level as long as subjects are maintained at a ferritin >100 ng/mL and TSAT >20%.

The Steering Committee (Section 10.8.4) will monitor blinded subject iron data in an ongoing fashion to ensure compliance.

6.12. Rescue Therapy

A rescue algorithm is provided to minimize subjects having an inadequate response to the treatment for their anemia for an extended period of time and to enable consistency in the application of rescue therapy across the study. Details are provided in Table 6.

This rescue algorithm **does not** apply to subjects with a low Hgb as a result of an acute or subacute event with an identifiable cause (e.g., GI bleed, blood loss due to surgery or vascular access). In these cases, treatment should be directed to the specific cause and randomized treatment will be continued. If a subject is transfused as part of the treatment, then the randomized treatment will be maintained at the current dose (unless Hgb is ≥ 12 g/dL which requires a dose hold).

Table 6 Rescue Algorithm for Anemia Management

Evaluate Subject for Rescue if: HemoCue Hgb remains <9 g/dL (at a scheduled study visit, Week 4 onwards) despite three ¹ consecutive dose increases above the starting or post-rescue ² dose (where HemoCue Hgb is <9 g/dL prior to each dose increase) OR HemoCue Hgb is <7.5 g/dL despite a dose increase at the prior study visit.	
Step 1: Initial Intervention	While continuing randomized treatment (increase dose if HemoCue Hgb <7.5 g/dL; otherwise maintain current dose), intervene with one or more of the following as dictated by clinical comorbidities 
 - Single course of IV iron up to 1000 mg (in addition to the iron management criteria) - Transfusion of up to two units of packed red blood cells (PRBC) if clinically indicated - Allow additional 4 weeks on randomized treatment (NOTE: this is a required choice; can be combined with either or both of the above).
Step 2: Rescue	Check HemoCue Hgb 4 weeks ± 1 week from last study visit; earlier checks of Hgb may be obtained to advise further intervention as clinically indicated. Randomized treatment should be permanently discontinued and the subject should be rescued according to local clinical practice if either, 
 - If HemoCue Hgb remains <9 g/dL despite initial intervention based on the average of two HemoCue Hgb values³ OR 
 - More than two units of PRBC were needed for transfusion (and was not related to acute bleeding).

1. Two consecutive dose increases if starting/post-rescue dose is daprodustat 12 mg or darbepoetin alfa 200 µg over 4 weeks; one dose increase if starting/post-rescue dose is daprodustat 16 mg or darbepoetin alfa 300 µg over 4 weeks; and no prior dose increase if starting/post-rescue dose is daprodustat 24 mg or darbepoetin alfa 400 µg over 4 weeks (top dose)
2. For subjects who previously were evaluated for rescue and who are able to continue in the trial, “post-rescue” dose is the dose of randomized treatment that a subject is receiving at the study visit after initial intervention.
3. Repeat HemoCue Hgb at the same study visit to confirm Hgb (using the same sample); take average of 2 values.

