5.5. Permanent Discontinuation of Randomized Treatment

Every effort should be made to keep subjects in the study including those who permanently stop randomized treatment and those that transition to dialysis. A subject may permanently discontinue randomized treatment at any time at his/her own request, or at the discretion of the investigator for safety or compliance reasons. A subject must permanently discontinue randomized treatment for the pre-specified reasons below.

- Kidney transplant.
- Meets criterion to receive rescue (Section 6.12).
- Becomes pregnant or intends to become pregnant during the study.
- Liver chemistry abnormalities exceeding the threshold criteria (Section 7.4.12).
- Diagnosis of cancer (new or recurrent), with the exception of localized squamous cell or basal cell carcinoma of the skin.
- Need for more than 14 days use of prohibited medication (Section 6.10.2).
- **ADPKD subjects only:** following further imaging, condition of the cystic disease in the kidney(s) has worsened more than expected given the clinical scenario and no other cause for the kidney function decline and/or cyst enlargement can be identified (Section 7.4.10).

Note: Subjects starting dialysis should not be withdrawn from the study and should continue randomized treatment as per protocol (Section 6.13).

In all cases, the reason for randomized treatment discontinuation and the date of the last dose will be recorded in the subject's electronic case report form (eCRF) and the subject will continue in the study as described in Section 5.5.1.

Subjects may be reapproached about restarting randomized treatment in certain circumstances if the sponsor and the investigator agree.

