12.6. Appendix 6: Randomized Treatment Dose Adjustment Schemes

HemoCue Hgb (g/dL) at current study visit ¹	HemoCue Hgb change since last study visit ¹	Randomized Treatment Dose Adjustment ⁵
<7.5 ²	Any change	Repeat Hgb and average values ⁶ ; if confirmed, increase to the next higher dose step
7.5 to <9.5	Decreasing or No change ⁷	Increase to the next higher dose step
7.5 to <9.5	Increasing ⁸	Maintain dose
≥9.5 to <10 at two consecutive visits	Decreasing or No change	Increase to the next higher dose step
≥9.5 to ≤11.5	Any change	Maintain dose
>11 to ≤11.5 at two consecutive visits	Increasing or No change	Decrease to the next lower dose step
>11.5 to <12	Decreasing	Maintain dose
>11.5 to <12	Increasing or No change	Decrease to the next lower dose step
≥12 ³	Any change	Repeat Hgb and average values ⁶ ; if confirmed, temporary hold the dose and re-check Hgb at next study visit ¹ ; restart at one dose step lower when Hgb <11.5 g/dL and provided it has been at least 2 weeks from the prior study visit
Any	>2 g/dL increase over 4 weeks (>1 g/dL increase over 2 weeks ⁴)	Repeat Hgb and average values ⁶ ; if confirmed, decrease to the next lower dose step
Any	>2 g/dL decrease over 4 weeks (>1 g/dL decrease over 2 weeks ⁴)	Repeat Hgb and average values ⁶ ; if confirmed, increase to the next higher dose step

1. "Study visit" refers to mandated study visits (every 4 weeks through Week 52; then every 12 weeks). From Week 52 onwards, additional study visits to check Hgb and dispense randomized treatment (where directed by the IRT system) are required under the following circumstances (additional visits have a visit window of ±1 week):
 - When Hgb at study visit is outside of the target range, i.e., <10 or >11 g/dL: Visit 4 weeks later to assess for dose adjustment.
 - When the dose of randomized treatment is changed or restarted: Visits every 4 weeks for 12 weeks.
 - When a medication that is a moderate CYP2C8 inhibitor (i.e., clopidogrel, teriflunomide, deferiasirox) is started, stopped, or the dose is changed: Visits every 4 weeks for 12 weeks.
 - When the investigator determines it clinically necessary to evaluate a subject sooner than 12 weeks later: Visit 4 weeks later to assess for dose adjustment.
 - For subjects transitioning to dialysis: Visits every 4 weeks for 12 weeks.
 - For subjects changing dialysis modality from HD to PD: Visits every 4 weeks for 12 weeks.

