2. This rule applies to any mandated visit or unscheduled visit, provided it has been at least 2 weeks from the prior study visit.
3. This rule applies to any mandated or unscheduled visit.
4. This rule applies to Week 2 and Week 4 visits only.
5. Those receiving the highest dose of randomized treatment who require a dose increase will maintain the same dose, while those receiving the lowest dose of randomized treatment that require a dose decrease will have doses withheld.
6. Repeat HemoCue Hgb at the same study visit to confirm Hgb (using the same sample) and take average.
7. No change may be redefined as an increase of <0.5 g/dL based on the review of blinded instream aggregate Hgb data.
8. Increasing may be redefined as an increase of ≥0.5 g/dL based on the review of blinded instream aggregate Hgb data.

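### The rescue rule is keyed to the starting dose, so some subjects failing on the top dose can never meet the Hgb <9 trigger while they stay there

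*Protocol*

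**What the plan says.** Protocol Section 6.12 says the rescue algorithm exists to limit prolonged inadequate response and "to enable consistency in the application of rescue therapy across the study".

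Table 6 gives two ways into rescue evaluation:

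- **Hgb <9 trigger.** Hgb is still below 9 g/dL at a scheduled visit after three consecutive increases above the starting or post-rescue dose. Only some increases count: "where HemoCue Hgb is <9 g/dL prior to each dose increase".
- **Hgb <7.5 trigger.** "HemoCue Hgb is <7.5 g/dL despite a dose increase at the prior study visit".

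Footnote 1 lowers the count from three to two for a starting or post-rescue dose of daprodustat 12 mg or darbepoetin 200 µg. Further up the ladder it requires "one dose increase if starting/post-rescue dose is daprodustat 16 mg or darbepoetin alfa 300" µg, and "no prior dose increase if starting/post-rescue dose is daprodustat 24 mg or darbepoetin alfa 400" µg. Footnote 2 defines a post-rescue dose only for subjects who have already been through a rescue evaluation.

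Appendix 6 governs titration. It raises the dose when Hgb is 7.5 to below 9.5 and falling or unchanged, and also when Hgb is "≥9.5 to <10 at two consecutive visits" and not rising. Footnote 5 adds: "Those receiving the highest dose of randomized treatment who require a dose increase will maintain the same dose".

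**The concern.** The two sets of rules do not fit together. Appendix 6 uses up dose steps at Hgb 9 to below 10, but Table 6 counts only steps taken below 9. Once the ladder is exhausted, no further counting increase is possible, and footnote 1 offers no relief because it looks back to the starting dose.

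The subjects left out are those on the maximum dose with Hgb still falling, which is the situation the algorithm was written for. Without a trigger they do not enter Step 1 or Step 2 of Table 6. The mandatory stop in Section 5.5 for meeting the rescue criterion is then not reached either. They are also not events in the secondary endpoint in Appendix 2 of time to stopping treatment under the rescue criteria.

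**Working it through.** **Footnote 1 reproduced.** The stated counts equal min(3, dose steps left from the starting dose to the top dose).

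- Darbepoetin (Table 5 ladder: 20, 30, 40, 60, 80, 100, 150, 200, 300, 400 µg): from 100 µg, min(3, 4) = 3; from 150, min(3, 3) = 3; from 200, 2; from 300, 1; from 400, 0.
- Daprodustat: from 12 mg, 2; from 16 mg, 1; from 24 mg, 0.

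So the footnote already accepts that increases which cannot be given should not be demanded. It applies this to the dose at the start, not to the dose reached.

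**Who can benefit on a first evaluation.** The full exemption (count 0) covers 1 of 10 darbepoetin steps and 0 of 3 daprodustat starting doses, since Section 4.4.1 gives those as 1, 2 or 4 mg. For daprodustat, the relaxations at 12, 16 and 24 mg can apply only after an earlier rescue evaluation.

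**Rule traces.** Visits are 4-weekly, the first Hgb is Day 1, and the Week 2 visit is left out. The Hgb paths are illustrative. The daprodustat step list is missing from the extracted text, so path F assumes 1, 2, 4, 6, 8, 12, 16, 24 mg from the doses in Section 6.1.

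| Path | Start | Hgb by visit | Reaches top dose | Counting / required | As written | With the fix |
|---|---|---|---|---|---|---|
| A | darbepoetin 100 µg | 9.4, 9.3, 9.2, 8.9, 8.7, 8.5, 8.2, 7.9, 7.3 | Week 16 | 2 / 3 | no trigger, Weeks 20–32 | Week 20 (8.5) |
| B | darbepoetin 200 µg | 9.2, 8.9, 8.7, 8.5 | Week 8 | 2 / 2 | trigger, Week 12 | – |
| C | darbepoetin 400 µg | 9.2, 8.9 | at start | 0 / 0 | trigger, Week 4 | – |
| D | darbepoetin 300 µg | 9.4, 9.2, 8.8, 8.4, 7.4, 7.2 | Week 4 | 0 / 1 | no trigger, Weeks 8–20 | Week 8 (8.8) |
| E | darbepoetin 200 µg | 9.4, 9.2, 8.9, 8.6, 8.2, 7.4, 7.2 | Week 8 | 1 / 2 | no trigger, Weeks 12–24 | Week 12 (8.6) |
| F | daprodustat 4 mg | 8.9, 9.4, 9.3, 9.2, 9.1, 8.9, 8.7, 8.5, 8.2, 7.9, 7.3 | Week 24 | 2 / 3 | no trigger, Weeks 28–40 | Week 28 (8.5) |

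Path A step by step: 100→150 at 9.3, 150→200 at 9.2, 200→300 at 8.9, 300→400 at 8.7. Two of the four steps were taken at 9 or above, so 4 − 2 = 2 count, one short of three.

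**A against B.** Both are at 400 µg with Hgb 8.5, and in both the last two increases were made at 8.9 and 8.7. B is evaluated and A is not, because the starting dose changes the required count.

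**The <7.5 trigger.** In path A with Hgb 7.4 at Week 20, it fires, because the dose was raised at Week 16. At Week 32 (7.3) it does not, because the dose was not raised at Week 28.

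**Ladder check.** If a 10 mg step exists and path F gains one more increase at Hgb 9.0, the result is the same four weeks later.

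**The case against.** - **Care is not blocked.** Section 5.5 lets treatment be stopped "at the discretion of the investigator for safety or compliance reasons", and iron and transfusion remain available. This stands and limits the clinical consequence. But discretion at each site is the variation Section 6.12 set out to reduce.
- **Counting only increases made below 9 may be a deliberate test of treatment failure, and one written rule for both arms is consistent.** That is reasonable while steps remain. It does not explain why a subject who starts on 400 µg needs no increase while one titrated to 400 µg may need a step that does not exist.
- **A withheld increase at the top dose could be read as an increase.** The text does not say so. Appendix 6 footnote 5 calls it maintaining the dose, and footnote 1's top-dose exemption would then be unnecessary.
- **A and B are not otherwise identical.** True: A has had four increases and B two, and A reaches Hgb 8.5 at Week 20 rather than Week 12. On the inputs Table 6 uses, both have two counting increases and only the required number differs.
- **The paths are invented, and the drops of 1.0 in D (8.4 to 7.4) and 0.8 in E (8.2 to 7.4) could have an acute cause, which Section 6.12 excludes.** The frequency is indeed unknown. A and F decline more gradually, by at most 0.6 between visits once on the top dose, and show the same gap.
- **The fix evaluates some subjects early.** D would be evaluated at Week 8 after one increase, and F four weeks after reaching 24 mg, although Section 4.4.1 puts steady state at almost 3 months. This is a real cost. However, footnote 1 already lets a 400 µg starter be evaluated at Week 4 (path C), and Step 1 requires four more weeks on treatment before any rescue stop.

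**Conclusion.** The gap is real on the current text and exists in both arms. It is confined to subjects who reach the top dose with fewer counting increases than footnote 1 requires. Those with enough increases below 9, or whose starting or post-rescue dose is itself the top dose, are covered.

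Its size cannot be given. The traces show what the rules do, not how often it happens. The direction of any effect on the arm comparison is also unknown. In each of the four gap paths there are four consecutive visits on the top dose with Hgb below 9 and no trigger.

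The consequence is limited. Only the time-to-rescue secondary endpoint, which has no multiplicity adjustment, is touched; no co-primary or principal secondary analysis depends on the trigger. The reason to correct it is that it works against the stated aims of Section 6.12 and the correction is small. The darbepoetin result rests on Table 5 alone; the daprodustat example rests on the assumed ladder.

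**What to change.** Add one sentence to Table 6 footnote 1: for a subject whose current dose is the top dose (daprodustat 24 mg or darbepoetin alfa 400 µg over 4 weeks), and has been since at least the prior study visit, no prior dose increase is required, and the subject is evaluated for rescue if HemoCue Hgb is below 9 g/dL at a scheduled visit, which includes values below 7.5. Keep the Section 6.12 exclusion of acute and subacute causes, and program the same rule in the IRT system for both arms.

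The cost is one sentence and one IRT rule; dose and HemoCue Hgb are already collected. There would be more rescue evaluations and, through Step 2, more permanent discontinuations, in unknown number. The time-to-rescue endpoint would count these subjects only from the amendment date, so its follow-up would span two rescue rules, and the report should say so.

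### Table 6 footnote 1 waives any prior dose increase for a subject whose starting or post-rescue dose was the top dose, even after that subject has been reduced below it

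*Protocol*

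**What the plan says.** Table 6 in Section 6.12 sends a subject for rescue evaluation when "HemoCue Hgb remains <9 g/dL (at a scheduled study visit, Week 4 onwards") despite three consecutive increases above the starting or post-rescue dose (the reference dose below), each made at Hgb under 9 g/dL. A separate limb covers Hgb under 7.5 g/dL despite an increase at the previous visit.

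Footnote 1 lowers the three increases to two for a reference dose of daprodustat 12 mg or darbepoetin 200 µg, and to one for 16 mg or 300 µg. It then asks for "no prior dose increase if starting/post-rescue dose is daprodustat 24 mg" or darbepoetin 400 µg, which it labels the top dose. Footnote 2 says that the post-rescue "dose is the dose of randomized treatment that a subject is receiving at the study visit after initial intervention".

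In Step 1 the site intervenes as follows: "While continuing randomized treatment (increase dose if HemoCue Hgb <7.5 g/dL; otherwise maintain current dose"). In Step 2, if Hgb is still under 9 g/dL about 4 weeks later, "Randomized treatment should be permanently discontinued and the subject should be rescued according to local clinical practice". Section 5.5 lists "Meets criterion to receive rescue (Section 6.12") among the mandatory reasons to stop, and adds: "Subjects may be reapproached about restarting randomized treatment in certain circumstances if the sponsor and the investigator agree".

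Appendix 6 can move a subject down from any dose. At Hgb 7.5 to below 9.5 g/dL and falling or unchanged, its instruction is to "increase to the next higher dose step"; if Hgb is rising, the dose stays.

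**The concern.** The zero-increase tier depends only on the reference dose. Footnote 2 fixes the post-rescue dose at one visit, the starting dose is fixed by nature, and nothing in Table 6 or Appendix 6 resets either after a reduction. The evident reason for asking no increase is that none is possible, but that reason lapses once the subject is on a lower dose.

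In every other tier the required increases must lie above the reference dose, so a reduced subject has to climb back past it before the 9 g/dL limb applies. Only the top-dose tier loses that protection. Step 1 then holds the dose at Hgb 7.5 g/dL or more, displacing the increase that Appendix 6 would order when Hgb is not rising.

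At stake is a mandatory stop for inadequate response before the available higher doses have been retried. Each such stop is an event in the time-to-rescue secondary endpoint of Appendix 2. Reach differs by arm: daprodustat starts at 1, 2 or 4 mg, so 24 mg can only be a post-rescue dose, whereas darbepoetin can also start at 400 µg.

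**Working it through.** **Inputs.** Upper darbepoetin steps: 150, 200, 300, 400 µg per 4 weeks (Table 5). Upper daprodustat steps: 12, 16, 24 mg (Section 6.1). Scheduled visits: every 4 weeks to Week 52, then every 12 weeks (Table 7). Dose moves: Appendix 6.

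**The plan's own counts.** Required increases = min(3, steps above the reference dose).
- 200 µg or 12 mg: min(3, 2) = 2.
- 300 µg or 16 mg: min(3, 1) = 1.
- 400 µg or 24 mg: min(3, 0) = 0.
- 150 µg: min(3, 3) = 3.

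These reproduce footnote 1. For reference doses of 150, 200 and 300 µg, the required increases end exactly at 400 µg.

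**Worked course (illustrative).** Hgb 10.2, 8.8, 8.7, 8.7 g/dL and so on at 4-weekly scheduled visits V0, V1, V2, V3 and later. Weeks are counted from V1, the first low visit. The word *remains* is read in its ordinary sense, as needing an earlier low visit.

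Reference 400 µg, now 200 µg after two reductions:
- Current text: V1 raised to 300; V2 evaluated, held at 300; V3 stopped.
- If the top dose had to be current: V1 300; V2 400; V3 evaluated; V4 stopped.

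| Reference dose | Dose at V0 | Current text | If top dose must be current |
|---|---|---|---|
| 400 µg | 300 µg | 8 weeks, on 400 µg | 8 weeks, on 400 µg |
| 400 µg | 200 µg | 8 weeks, on 300 µg | 12 weeks, on 400 µg |
| 400 µg | 150 µg | 8 weeks, on 200 µg | 16 weeks, on 400 µg |
| 200 µg | 200 µg | 12 weeks, on 400 µg | unchanged |
| 150 µg | 150 µg | 16 weeks, on 400 µg | unchanged |

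So two reductions leave one step unused, three leave two, and one reduction leaves none.

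**Slower fall.** Hgb 9.8, 9.2, 8.9, 8.8, 8.8. Appendix 6 raises the dose at 9.2 and again at 8.9, and evaluation comes at the first 8.8. From 200 µg the subject is back on 400 µg by then: no anomaly. From 150 µg the stop is on 300 µg.

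**After Week 52.** Rescue is evaluated at scheduled visits, now 12 weeks apart. The added 4-weekly visits of Appendix 6 sit in the unscheduled column of Table 7, which has no rescue-medication entry. A subject on 150 µg whose first low value falls at a scheduled visit goes to 200 µg then, 300 µg at 4 weeks and 400 µg at 8 weeks, and is evaluated at 12 weeks on 400 µg. The path stays open mainly when the first low value falls at an added visit shortly before a scheduled one.

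**Who can start at 400 µg.** With rounding to the nearest study dose (Section 6.3.2), the cut is (300 + 400) / 2 = 350 µg per 4 weeks. Assuming the Table 4 ratio of 250 U per µg also applies to the darbepoetin start, that is 350 × 250 / 4 = 21,875 U/week of IV epoetin.

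**The case against.** - **Stopping below the top dose is normal here.** Correct. A 2 mg daprodustat starter is evaluated at 8 mg after three increases, with four steps unused; a 30 µg darbepoetin starter at 80 µg, with five unused. A reader might infer that any stop with higher steps left is an error. The protocol does not support that: Table 6 never requires the ladder to be exhausted. The anomaly is only that one tier requires no increase after a reduction.
- **The top-dose label shows that current top-dose subjects were meant.** Probably so, and many investigators would read it that way. But the label attaches to the starting or post-rescue dose, and Section 7 allows no waivers except for immediate safety concerns. If that was the intent, the text should say it.
- **Most paths close.** This largely stands, as the slower fall and the schedule after Week 52 show. Low Hgb from an acute or subacute event with an identifiable cause is also excluded, which removes some rapid falls. A reader might infer that one reduction is enough, or that two always are. One suffices only if the first low visit already counts as *remaining* low, a strained reading; the stop would then come at 4 weeks on 300 µg. Two suffice only with a rapid fall.
- **Little follows from it.** Evaluation leads first to Step 1, and Section 5.5 allows an agreed restart. This too stands, and limits the severity.

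**Conclusion.** The point holds as a minor flaw in a stated rule. As written, footnote 1 can lead to a mandatory stop with one or two darbepoetin steps unused in the worked cases, where subjects with reference doses of 150 to 300 µg would have been raised to 400 µg first.

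On the ordinary reading of *remains*, it arises mainly in the first 52 weeks, after two reductions with a rapid fall or after three or more. The subject must have started on the top dose or left an earlier evaluation on it, and must stay under 9 g/dL through Step 1. The number affected is probably small and cannot be estimated from the protocol. The Hgb courses used are illustrations, not expected data.

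A reader might infer that the co-primary results or their power are at risk. They are not: Sections 9.1.1 and 9.1.2 count subjects regardless of later treatment, discontinuation or rescue. The endpoint touched is time to rescue, and Section 9.4.2.1 treats the additional secondary analyses as exploratory.

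**What to change.** In footnote 1, after the top-dose tier, add: *and the subject is currently on that dose; a subject since reduced below it follows Appendix 6 increases until back at the top dose before the Hgb <9 g/dL criterion can trigger evaluation.* Leave the counts of three, two and one, the 7.5 g/dL limb and Steps 1 and 2 as they are.

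The cost is one clause, plus the matching IRT rule if the IRT flags rescue. No new data are needed. Nothing changes for subjects still on the top dose, or whose reference dose is below it.

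For a subject reduced k steps, evaluation comes at least 4(k−1) weeks later: 0, 4 and 8 weeks for k = 1, 2 and 3. That is a minimum on 4-weekly visits. Appendix 6 keeps the dose when Hgb is rising, so a subject fluctuating 8.6, 8.7, 8.6, 8.7 g/dL would be raised only at alternate visits, unless the redefinition allowed by its footnotes 7 and 8 is in force. The extra time under 9 g/dL is a real cost, given the algorithm's aim of limiting prolonged inadequate response. The 7.5 g/dL limb and the investigator's discretion to stop under Section 5.5 apply throughout.
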